## DECIDE Parent-Provider Interaction IRB Protocol

### **8.0 Study Withdrawal/Discontinuation**

After signing the informed consent, participants can withdraw and leave the study at any time. Members of the study team will assist participants in withdrawing if that is the wish of the participant. Withdrawing from the study will not impact the participant's healthcare in any way.

### **9.0 Statistical Considerations**

We will calculate the proportion eligible that enroll and proportion completing the intervention for both parents and providers. We will tabulate responses to Parent and Provider Satisfaction with Intervention items and calculate the proportion of parents and providers who have a mean ratings of at least 4 on the 5-point scale (satisfied or highly satisfied). Effect sizes will be estimated by fitting linear mixed models, with parent, provider, or observer target and outcomes variables, all measured at T2, as outcomes and treatment group (intervention or usual care) as the explanatory variable. All models will also include the T1 outcome as a covariate and random effects for provider and parent nested within provider to account for clustering. Effects sizes will be estimated with  $\omega^2$ . Analyses will be intent-to-treat and conducted using SAS Version 9.4 (SAS Institute Inc., Cary, N.C., Copyright 2002-2012).

*Supplementary Analyses:* We will investigate how the adjustment for covariates (age of child, sex of provider and parent, parent race and income, severity of child illness and duration in treatment) impacts effect size estimates by adding interaction terms to models and estimating effect sizes separately for different levels of the covariate (e.g. male and female for parent gender). *Missing Data:* We will compare baseline variables between subjects who drop out of the study to those who do not using two-sample *t* tests, chi-square tests or their non-parametric equivalents as appropriate. If we find that the missing data appear to be MNAR, this information will be used in designing the larger trial. Because of the relatively small sample size, we will not attempt to model the missing data mechanism in this pilot study. *Sex as a biological variable:* As noted above, we will estimate effect sizes by sex for all outcomes. [name] will lead the qualitative analysis of the semi-structured interviews with input from PI and research team. The interviews will be coded with standard content analytic procedures.

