### **Randomization**

All participants will be assigned to the intervention arm and there will be no randomization. Instead, the intervention results will be compared to historical data.

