### Phase II, Aims 2 and 3.

**Design.** A pilot trial to assess feasibility and estimate outcomes in intervention vs. an historical control.

**Setting.** Similar to preliminary studies, we will conduct this trial at Sandra Eskenazi Mental Health Hospital in Indianapolis, IN, Bowen Center in Indianapolis, IN, Centerstone centers in Indiana, Florida and Tennessee, other applicable mental health centers and private practice in the US. Midtown is the largest publicly funded mental health center in Indiana and serves primarily low income and/or minority population (see Facilities and Resources). Child and Adolescent Program employs 22 masters-prepared mental health providers. [name] also has clinical privileges at Midtown to facilitate recruitment (see support letter). Midtown has named treatment engagement as a top strategic priority.

**Sample.** First, we will recruit 16 providers and then work with them to invite parents (or parent surrogates) of adolescents aged 6 to 17 years who have been diagnosed with a DIC disorder. Ideally, we will enroll 80 parents (5 parents per enrolled provider).

**Sample size justification.** Because this is a feasibility pilot study, statistical models will be fit to estimate effect sizes for use in a future randomized trial. Any inferential testing is considered exploratory though effect sizes of  $\geq 0.65$  could be detected with 80% power in the models described below assuming pre/post exposure correlation of 0.5, intraclass correlation of 5%, and two-tailed test ( $\alpha=0.05$ ). We will follow the recommendation of Hertzog that a minimum of 30 participants per group are needed for pilot studies to examine group comparisons. To account for potential 20% dropout, we will recruit 40 parents to the intervention group with 1-5 parents per provider) for up to a total of 80 parents. Provider sample size is based on availability.

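### Omega-squared is the only effect measure named for Aim 3: it is unsigned, off the scale on which 0.65 reproduces, and varies with group ratio; the SAP names no effect estimate in its place

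*Protocol*

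**What the plan says.** The sample size justification in Section 6.0 of the protocol gives the purpose of the models: "statistical models will be fit to estimate effect sizes for use in a future randomized trial". It adds that "effect sizes of $\geq 0.65$ could be detected with 80% power", without naming the metric of the 0.65.

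Section 9.0 models the T2 outcome with "treatment group (intervention or usual care) as the explanatory variable". It continues: "All models will also include the T1 outcome as a covariate and random effects for provider and parent nested within provider". The sentence on effect measures then reads "Effects sizes will be estimated with" omega-squared. No signed difference, standardised difference or confidence interval is mentioned. The supplementary analyses estimate effect sizes by covariate level and by sex.

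The hypotheses in Section 3.0 all have a direction: greater improvement for parents and providers, and higher retention for adolescents. Under Randomization in Section 5.0 there is a single recruited arm, and "the intervention results will be compared to historical data". The protocol does not give the size of the historical group.

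The SAP says the protocol's analysis was changed because the design became pre/post. It calculates change scores and tests them with a paired t-test or a Wilcoxon signed-rank test. Because only 3 parents had paired data, it tests provider and provider-substudy outcomes only. It names no effect size and no interval.

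**The concern.** A pilot meant to supply planning values needs an effect measure that shows which way the outcome moved and that carries over to a trial with a different allocation. Omega-squared is a share of variance explained. A benefit and an equal harm give the same population value, and in the supplementary analyses opposite effects in two subgroups would look alike. It cannot be set directly beside the 0.65. It also depends on the ratio of the groups compared, which here is unknown and may be far from the 1:1 of a typical randomised trial. The risk is that Aim 3 reports a number without direction that is then misread at the planning stage.

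**Working it through.** **Inputs.** From the sample size justification: 40 parents recruited to the intervention group, 20% dropout, pre/post correlation r = 0.5, ICC = 0.05, two-tailed alpha 0.05, 80% power, effect 0.65. The protocol gives 5 parents per provider as the ideal, and elsewhere 1 to 5. *Assumptions:* 32 in each group for the power check; 4 parents per provider (5 less 20%); historical groups of 64, 100 or 200.

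**Step 1: reproduce 0.65.** Evaluable parents: 40 × 0.8 = 32. Design effect: 1 + (4 − 1) × 0.05 = 1.15. Detectable standardised difference with T1 as covariate:

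(1.960 + 0.842) × √[(2/32) × (1 − 0.5²) × 1.15] = 0.6505, with power 79.9% at 0.65.

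So 0.65 reproduces as a standardised mean difference. With 5 parents per provider the result is 0.664 (power 78.3%), so the match depends on the cluster size, which the protocol does not state for this calculation.

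**Step 2: convert to omega-squared.** Let p be the share of participants in one group. After T1 adjustment and ignoring clustering:

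f² = p(1 − p)d² / (1 − r²), and ω² = f² / (1 + f²).

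At 1:1, f² = 0.25 × 0.4225 / 0.75 = 0.1408 and ω² = 0.123. Since d enters squared, d = −0.65 gives the same 0.123. In 8,000 simulated data sets per setting with 32 per group, true effects of +0.65 and −0.65 gave mean ω² of 0.119 and 0.118, while the group coefficient averaged +0.65 and −0.65. A sample ω² can fall below zero (about 67% of the time when there is no effect), but that does not indicate harm.

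**Step 3: vary the group ratio with d held at 0.65.** The column of apparent d reads ω² as if the groups were equal: d = 2√(0.75 f²). The size per arm is 2 × (1.960 + 0.842)² × 0.75 / d² = 11.77 / d², rounded up (80% power, T1-adjusted, no clustering).

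| Intervention : historical | f² | ω² | Apparent d if read as 1:1 | Per arm |
|---|---|---|---|---|
| 32 : 32 | 0.141 | 0.123 | 0.65 | 28 |
| 32 : 64 | 0.125 | 0.111 | 0.61 | 32 |
| 32 : 100 | 0.103 | 0.094 | 0.56 | 38 |
| 32 : 200 | 0.067 | 0.063 | 0.45 | 59 |

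Converting back with the actual p returns |d| = 0.65 and 28 per arm in every row. Without T1 adjustment the pattern is the same: 38 per arm at 1:1 becomes 42 at 2:1 and 95 at 8:1 if misread.

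**The case against.** The strongest objection is that this analysis has been superseded. The SAP has no group term and so no group ratio, its change scores carry a sign, and with 3 parents having paired data a comparison of 32 parents with a historical group is hypothetical. That is largely right, and it limits the practical weight of the table above. It does not supply what is missing: the SAP commits only to tests, so the estimation purpose stated in the protocol is served by omega-squared or by nothing.

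A reader might also infer that omega-squared makes the directional hypotheses unanswerable and the result useless for planning. The documents do not support this. The Section 9.0 model yields a signed, T1-adjusted group coefficient; the plan simply does not commit to reporting it. Omega-squared converts back to the absolute difference once the group ratio and variance basis are known, so the inflated sizes arise only if a planner assumes 1:1. At 2:1 even that error is small (32 against 28).

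Nor is every result in Section 9.0 expressed this way: enrolment, completion and satisfaction are reported as proportions. Finally, the metric of 0.65 is inferred from the arithmetic, not stated.

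**Conclusion.** The point holds as a minor reporting weakness. Two parts rest on no assumed group size: omega-squared does not show direction, and neither document commits to a signed effect estimate with an interval. That 0.65 is on another scale rests on the reproduction in Step 1, which needs 4 parents per provider. The planning distortion (32, 38 or 59 per arm instead of 28) rests on assumed historical group sizes and on a reader who ignores the ratio. It shows what could go wrong and is not a forecast. The documents also leave open whether the historical comparison is still to be made at all.

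**What to change.** - **Section 9.0, wherever the historical comparison is kept.** For continuous outcomes, report the T1-adjusted mean difference in scale units, and the same difference divided by the pooled T1 standard deviation, signed so that positive means improvement, each with a 95% confidence interval. Omega-squared may stay as an optional extra.
- **Retention (Hypothesis 3.3).** Table 1 defines this as attending a minimum number of visits, so it is binary and a T1-adjusted mean difference does not suit it. Report a difference in proportions with a 95% confidence interval.
- **SAP, provider and provider-substudy analyses.** Report the mean change and the standardised mean change with 95% confidence intervals alongside the tests.
- **Sample size justification.** State that 0.65 is a standardised mean difference, and give the cluster size used.
- **Reconciliation.** Bring the Randomization text, the Phase II design and sample size text and Section 9.0 into line with the SAP on whether a historical comparison is still made.

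The cost is slightly more reporting and a few sentences of text. No new data are needed.

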If study findings are positive, we will be poised to test the modified DECIDE in a fully-powered R01 level randomized, controlled, multi-site clinical trial. If study findings are negative, we will have process and outcome information needed to further refine DECIDE or pursue different interventions. Either way, this line of research has potential to optimize parent-provider interactions and ultimately, ensure adolescents with DIC receive the behavioral health care they need.

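### Must Section 9.0 be reworded because it provides for data that appear MNAR while naming only a baseline comparison of dropouts?

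*Protocol*

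**What the plan says.** Section 9.0 of the protocol deals with missing data in three steps. First, "We will compare baseline variables between subjects who drop out of the study to those who do not", by two-sample t tests, chi-square tests or non-parametric equivalents. Second, "If we find that the missing data appear to be MNAR, this information will be used in designing the larger trial". Third, "Because of the relatively small sample size, we will not attempt to model the missing data mechanism in this pilot study". The section names no other diagnostic and no sensitivity analysis.

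The larger trial is the one foreseen in Section 3.0, where positive findings mean that "we will be poised to test the modified DECIDE in a fully-powered R01 level randomized, controlled, multi-site clinical trial". The sample size justification in Section 6.0 gives the pilot the same purpose: "statistical models will be fit to estimate effect sizes for use in a future randomized trial". It also supplies the dropout figure: "To account for potential 20% dropout, we will recruit 40 parents to the intervention group".

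Information about dropout is also collected outside Section 9.0. The Aim 2 measures include logs of attrition and its reasons. Table 1 takes visit attendance and adolescent retention from the medical record. Under Intervention Fidelity, facilitators note each parent's engagement and understanding. The safety text in Section 7.0 has the committee monitor why people drop out, and a study representative telephones participants who withdraw.

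The SAP replaces the controlled comparison with pre/post tests of change scores and has no text on missing data. It reports that only 3 parents had both time points, so no parent outcome was tested.

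**The concern.** The first sentence names a diagnostic, the second anticipates a finding, and the third rules out modelling the mechanism. Read in sequence, they suggest that the baseline comparison is what would make the data appear MNAR. That inference would be invalid. MNAR means that, given what was observed, dropout still depends on the T2 values that were not seen, and baseline variables cannot reveal this.

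At stake is the information handed to the larger trial. Dropout fully explained by baseline, which a model adjusting for T1 handles, might be recorded as MNAR. Dropout that depends on the unseen T2 outcome might be passed over because the baselines look alike. Since the larger trial is the reason for running the pilot, the point deserves a check.

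**Working it through.** **The plan's own figures.** The protocol states a detectable effect of 0.65 at 80% power. The inputs are a pre/post correlation of 0.5, an intraclass correlation of 0.05 and two-sided alpha of 0.05. With 40 × 0.8 = 32 retained per group, and assuming two equal groups and 4 parents per provider (5 less 20%):

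(1.960 + 0.842) × √[(2/32) × (1 − 0.5²) × (1 + 3 × 0.05)] = 2.802 × √0.0539 = 0.65.

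The figure reproduces. The recommended minimum of 30 per group needs 30/0.8 = 37.5, so 38, and 40 covers it. None of this depends on the missing-data sentence.

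**What a baseline comparison can identify.** Let X be the baseline variables, Y the T2 outcome and R the indicator that Y is observed. MCAR means that P(R | X, Y) is constant. MAR means that it depends on X only. MNAR means that it depends on Y given X. The comparison of dropouts with the rest examines only whether P(R | X) is constant. For any MNAR mechanism, define π(X) as the average of P(R | X, Y) over Y given X. A MAR mechanism with dropout governed by π(X) gives exactly the same joint distribution of R and X, so every baseline test behaves identically under the two. No sample size separates them.

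**Illustration.** The dropout strengths below are assumptions, not figures from the documents. The setting is 40 parents (8 providers × 5), 20% dropout, T1–T2 correlation 0.5, intraclass correlation 0.05, logistic dropout with an odds ratio per SD of 2.72 (range 1.65 to 4.48), and 40,000 simulated trials per setting. The last column adds the seven covariates Section 9.0 lists ("age of child, sex of provider and parent, parent race and income, severity of child illness and duration in treatment"), simulated as unrelated to dropout.

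| Dropout depends on | T1 t test significant | At least one of 8 tests significant |
|---|---|---|
| Nothing (MCAR) | 5% | 34% |
| T1 (MAR) | 60% (22–86%) | 72% (46–90%) |
| T2 (MNAR) | 19% (9–29%) | 43% (36–50%) |
| Part of T2 not predicted by T1 (MNAR) | 5% | 34% |

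The 34% under MCAR agrees with 1 − 0.95⁸ = 0.337. A difference is 0.604/0.190 = 3.2 times as likely under MAR as under MNAR on T2 with the single T1 test, but only 0.720/0.431 = 1.7 times with all eight. With 80 parents and the strongest dropout, the single-test ratio is 0.990/0.531 = 1.9. The ratio therefore depends on the setting chosen. The identification argument does not.

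In separate runs of 10,000 trials with 40 or 80 parents, no clustering and a log-odds slope of 1.5 per SD, the baseline-adjusted mean among completers was unbiased under MCAR and MAR. It was off by about 0.18 to 0.20 SD under both MNAR mechanisms. The comparison thus fires most readily where adjustment already suffices.

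**What uses the label.** Section 9.0 fits mixed models with T1 as a covariate whatever the mechanism. The SAP computes post-minus-pre change scores and chooses a paired t test or a signed-rank test on the Shapiro–Wilk result. Neither branches on whether the data are called MNAR, and the sample size does not either. The sentence's only stated use is for the design of a trial that neither document specifies.

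**The case for a change.** The strongest argument for a change is that either reading leaves a fault. If the MNAR judgement rests on the baseline comparison, it is invalid. If it rests on something else, the plan does not say what. Informing the next trial is a stated aim, the SAP adds nothing on missing data, and one reworded sentence would cost no data and no analysis.

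The identification point stands in full. Three parts of the argument do not carry.

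- The link between the comparison and the judgement is read from adjacency. The protocol sets no test, threshold or rule by which data become MNAR, and its refusal to model the mechanism fits authors who know that a small pilot cannot establish it.
- The unstated basis has an obvious candidate. Logged reasons, withdrawal calls, session notes and visit records cannot prove MNAR, but they can reasonably prompt suspicion of it, and the hedged wording claims little more. A missing cross-reference to them is an editorial gap.
- A low cost does not make a gain. New wording would alter nothing the pilot computes or reports, and anything it said about MNAR in the larger trial would bind a study that will have its own protocol.

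**Conclusion.** No change to the plan is warranted. The sentence is loose: a baseline comparison is evidence about MCAR and about predictors of dropout, and it neither shows nor excludes MNAR. An analyst would report it that way, alongside the recorded reasons for dropout, and would leave MNAR to the larger trial's own planning.

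The effect on the pilot's results is zero. No estimate, test, sample size or decision depends on the label, and no parent outcome was tested. Whether the provider pre/post tests are themselves affected by dropout is a separate question that this sentence does not touch.

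The conclusion assumes that the MNAR remark serves only as background for the later trial, which is the sole use the protocol gives it. It does not rest on the simulated percentages, which depend on assumed dropout strengths.

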### **10.0 Privacy/Confidentiality**

A secure web-based system (REDCap) will be used to capture study data. Participation in this research is covered by a Certificate of Confidentiality from the National Institutes of Health. The researchers may not disclose or use any information, document, or specimens that could identify any participants in any civil, criminal, administrative, legislative, or other legal proceeding, unless participant consents to it.

### **11.0 Record Retention**

Records will be retained for up to seven years post study completion.

DECIDE Parent-Provider Interaction  
IRB Protocol

Modification and evaluation of the DECIDE intervention to improve parent-provider interactions in low-income parents of adolescents with Disruptive Impulse Control, and Conduct Disorders

NCT number: NCT04445155

Date: 12/13/2023

Statistical Analysis Plan for the DECIDE Parent-Provider Intervention Study

The statistical analysis plan was changed from the original statistical analysis plan in the protocol because the study design was changed. Originally, there was a control group planned (treatment as usual); Instead, the study design was changed to a pre/post design, with outcomes collected pre- and post-intervention for three sample populations: 1) Providers; 2) Parents; and 3) a second group of providers (referred to as Provider Substudy).

SAS version 9.4 (Cary, NC) was used for statistical analysis. The alpha level was set at 0.05 for all statistical tests. For each outcome, change scores were calculated as post-intervention score minus pre-intervention score. Next, the change scores were tested for normality using the Shapiro-Wilk test. If the change scores were not normally distributed, then a Wilcoxon signed-rank test was conducted to see if the distribution of the outcome data was different from pre- to post-intervention. If the change scores were normally distributed, then a paired t-test was conducted to test whether the mean difference was not equal to zero. As pre- and post-intervention outcome data was available for only 3 parents, there were no statistical analyses conducted with the parent outcome data; thus, statistical tests were only generated for the Provider and Provider Subgroup outcomes.

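### For the two provider samples the SAP specifies only tests at 0.05 and names no estimate or interval for the change, although Aim 3 is an estimation aim

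*SAP*

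**What the plan says.** **Protocol.** Aim 3 (Section 3.0) is to estimate preliminary effects on parent, provider and adolescent outcomes; its hypotheses are framed against usual care. The sample size justification (Section 6.0) says models are fitted to obtain effect sizes for a later randomized trial and that any inferential testing is exploratory. Section 9.0 specifies linear mixed models with treatment group as explanatory variable, the T1 value as covariate, and omega-squared as effect size.

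A historical comparison appears in Section 5.0 (Randomization) and in Section 6.0 under Design, the study schema, Aim 3 measures and Intervention Fidelity.

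**SAP.** It opens: "The statistical analysis plan was changed from the original statistical analysis plan in the protocol because the study design was changed". The new design is pre/post in three samples: providers, parents and a second provider group. For each outcome, "change scores were calculated as post-intervention score minus pre-intervention score". Then "the change scores were tested for normality using the Shapiro-Wilk test". Non-normal changes go to a Wilcoxon signed-rank test "to see if the distribution of the outcome data was different from pre- to post-intervention"; normal changes go to a paired t-test "to test whether the mean difference was not equal to zero". On level: "The alpha level was set at 0.05 for all statistical tests". On parents: "As pre- and post-intervention outcome data was available for only 3 parents", no parent analysis was done, so "statistical tests were only generated for the Provider and Provider Subgroup outcomes".

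**The concern.** An estimation aim is paired with an analysis described only as tests. The SAP calculates individual change scores, but only as input to a test, and the mean difference appears only as the quantity tested against zero. On the signed-rank branch no measure of location is named at all.

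At stake is what the pilot hands to the next trial. Section 3.0 ties the next step to whether findings are positive or negative. With few providers, a p-value above 0.05 may reflect little change or an imprecise estimate, and the p-value alone cannot separate the two. With no parent analysis, the provider samples are the only place where the SAP can contribute to Aim 3.

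**Working it through.** **1. Is an effect estimate specified for the analysis described?**

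| Source | Estimate named | Usable under the SAP as written? |
|---|---|---|
| Section 9.0 | omega-squared from a model with a treatment-group term | No. The SAP has a single group per sample and no comparator |
| Sections 5.0 and 6.0 | comparison with historical data | Not specified in the SAP, which does not mention historical data |
| SAP | none; paired t-test or signed-rank test at 0.05 | Tests only |

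The answer is no, and it rests on the text rather than on any calculation.

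**2. The protocol's own figure.** The sample size justification gives 0.65 as detectable with 80% power, with pre/post correlation r = 0.5, ICC = 0.05, two-tailed 0.05, and 40 intervention parents less 20% dropout, so n = 32 per group. I assume m = 4 analysed parents per provider (5 less 20%).

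d = (z0.975 + z0.80) × sqrt[(2/n)(1 − r²)(1 + (m − 1)ICC)]
= (1.960 + 0.842) × sqrt[(2/32)(0.75)(1.15)]
= 2.802 × 0.2322 = 0.650, with power 79.9% at 0.65.

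With m = 5 the result is 0.664 (power 78.3%). The figure reproduces, but only for a two-group parent model. It says nothing about one-sample provider changes: by the noncentral t distribution, a paired t-test has 36% power (n = 8) or 68% (n = 16) at a standardized change of 0.65.

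**3. Precision for provider change.** The SAP gives neither a provider n nor an SD. Section 6.0 says provider numbers depend on availability. I use two protocol figures as assumptions: 16 (Sample) and 8 (Aim 2 measures, possibly left from the two-arm design). In units of the SD of change, the 95% half-width is t(0.975, n − 1)/sqrt(n):

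- n = 8: 2.365/2.828 = 0.836
- n = 16: 2.131/4 = 0.533

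**4. What a p-value alone leaves out.** For the paired t-test, standardized change = t(1 − p/2, n − 1)/sqrt(n), and the interval is that value plus or minus the half-width.

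| Two-sided p | n | Change (SD) | 95% interval (SD) |
|---|---|---|---|
| 0.20 | 8 | 0.50 | −0.34 to 1.34 |
| 0.20 | 16 | 0.33 | −0.20 to 0.87 |
| 0.05 | 8 | 0.84 | 0 to 1.67 |
| 0.05 | 16 | 0.53 | 0 to 1.07 |

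The non-significant rows are compatible with a small fall, no change or a large gain.

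**5. Would a t interval be fit for the purpose?** Simulated coverage of the mean at n = 8 and n = 16 was 95.1% and 94.9% for normal changes, 93.6% and 94.1% at skewness 1, and 89.3% and 91.3% for exponential-type skew. It is adequate unless skew is strong. A Hodges-Lehmann interval keeps its level, but for the pseudomedian rather than the mean. With mean change 0, the pseudomedian lies at −0.08 SD for skewness 1 and −0.16 SD for skewness 2. The two coincide under symmetry.

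**The case against.** The strongest reply is that silence is not exclusion. The SAP is short, written in the past tense and describes tests; software usually prints the mean difference and its interval with a paired t-test. This stands as a limit. A reader might infer that only p-values were produced or reported, and the documents do not show that. The gap is in what is specified.

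Second, the missing estimate is not the sole reason Aim 3 goes unmet, though a reader might infer that it is. The comparator, the parent analysis and adolescent retention are also absent from the SAP, and adding intervals cures none of these.

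Third, one might say that the Section 9.0 effect size became impossible once the concurrent control was dropped. That is too strong: with suitable historical usual-care data its group term could in principle be fitted. But the documents do not describe those data and the SAP does not use them.

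Fourth, one might read the missing exploratory label as turning the tests into confirmatory ones. Nothing in the SAP withdraws the Section 6.0 statement. Repeating it is good practice, and its absence is a minor matter.

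Finally, the normality gate might be thought to inflate error. The working does not establish that in general, and the documents do not show that skew is present. The point does not rest on the gate.

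**Conclusion.** The point holds as a specification gap for the provider outcomes. The protocol calls for estimated effects with exploratory testing; the SAP limits the two provider samples to tests at 0.05 and names no estimate, SD or interval. Followed as written, it answers the trial's own question less well than the change scores it already calculates would allow.

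The size depends on assumed numbers: an unreported interval of roughly ±0.84 SD with 8 providers or ±0.53 SD with 16. These are illustrations, since the analysed n and the SD are not given.

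The repair reaches Aim 3 for provider outcomes only. Parent outcomes (3 pairs) and adolescent outcomes stay unaddressed, and a one-group change is not the usual-care contrast in the hypotheses. Nor does the SAP show that the Section 9.0 enrolment, completion and satisfaction summaries were withdrawn; it simply does not mention them.

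**What to change.** For every outcome in each provider sample, whichever test was selected, report:

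- the number of providers with both T1 and T2;
- mean change and SD of change;
- a 95% confidence interval for the mean change;
- a standardized change, preferably with the small-sample factor, about 1 − 3/(4(n − 1) − 1): 0.89 at n = 8 and 0.95 at n = 16.

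Where changes look skewed, a Hodges-Lehmann estimate with its interval can be added as an optional sensitivity analysis, labelled as a pseudomedian.

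In the SAP text, repeat that testing is exploratory, mark the additions as post hoc beside the tests already run, and say that an uncontrolled provider change is not the usual-care contrast in the Aim 3 hypotheses. Either state that the historical comparison was dropped, or reconcile the SAP with the parts of Sections 5.0 and 6.0 that keep it.

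The cost is a few table columns and some sentences, from change scores already calculated, with no new data. The downsides are that wide intervals will be on display, the t interval under-covers somewhat if changes are strongly skewed, and the additions carry post hoc status.
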